### **6.7 Duration of Study and Overview of Procedures and Protocol:**

Testing will occur over the course of a single day at the Fixel Institute for Neurological Diseases. Similar to new patient clinical evaluations, subjects will be instructed to withhold any PD, ET, or dystonia medications for 12 hours prior to testing. The study visit will last up to 4 hours and will include a variety of motor tasks and clinical tests (described in detail below) both on and off VTS. For Parkinson's disease and essential tremor patients, the devices will be worn on the wrist and/or ankles. For patients with dystonia, the devices will be adhered to the skin of the neck using medical grade double sided tape and a latex medical wrap. Patients with PD will undergo a more comprehensive testing evaluation, while patients with ET or dystonia will undergo a brief, more focused evaluation. Subject responses will not be compared across diseases given the preliminary nature of the research and analysis. Outcomes to be measured are described below in the order that they will be tested for each individual subject group (PD, ET, dystonia).

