## **6.4 Inclusion/Exclusion Criteria:**

### 6.4a. Inclusion criteria:

- Age 18-80 and able to provide informed consent.
- Have a diagnosis of Parkinson's disease, essential tremor, or cervical dystonia made by a movement disorders specialist.
- Medically optimized without planned medication changes for the duration of the study.
- For patients with ET, they will have a score of at least 2 on items 5 and 6 of the Fahn-Tolosa-Marin (FTM) Tremor Rating Scale.
- For patients with dystonia, they will have abnormal dystonic postures of the head and not isolated head tremor

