### 6.4b. Exclusion criteria:

- The presence of additional neurologic diseases, that might confound testing or the coexistence of PD and ET together (action tremor that was present prior to the development of parkinsonism).
- Symptoms of peripheral neuropathy at the wrist (reduced vibratory, pinprick, or temperature sensation)
- Montreal cognitive assessment (MoCA) score < 20 or previously documented dementia
- Unable to walk without a walking aid (e.g. cane, stick, walker)

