### **10. Possible Discomforts and Risks:**

In general, the risks are minimal for individuals who participate in this study. As the intensity of the vibration produced by the Vibrohealth device is far less than that which is produced by commercially available massagers that provide vibratory stimulation to the body, the incidence and severity of any adverse effects is expected to be limited, and no adverse events occurred in a previous trial using the Vibrohealth device in over 50 patients with PD and in our pilot testing at UF of 8 subjects. With regard to discomforts and risks, first the VTS stimulation could be annoying or unpleasant, and there is the possibility of minor skin irritation at the site where the wearable devices are placed.

Second, subjects will be asked to come to testing sessions OFF medications (as is done during standard-of-care initial clinic visits) in order to reduce confounding effects of medications, which could be temporarily uncomfortable. Third, patients may also find the tasks and scales tedious or boring. To minimize fatigue associated with completion of screening and tasks, subjects will be allowed to take frequent breaks to rest as needed. Patients will have the option of discontinuing testing at any time, and data that is partially collected may still be useful given the preliminary nature of the study. Though unlikely, it is possible skin irritation might persist outside of the testing period. Should this occur, the patient would be instructed to seek routine medical care. It is also possible that there are unknown risks for participating in this study.

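### Devices are fixed to the neck of dystonia patients with tape and a latex wrap, but no eligibility criterion addresses known latex or adhesive allergy and the risk section does not name it

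*Combined protocol and SAP*

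**What the plan says.** Section 6.7 describes two ways of attaching the stimulators. For two of the three groups: "For Parkinson's disease and essential tremor patients, the devices will be worn on the wrist and/or ankles". For dystonia: "the devices will be adhered to the skin of the neck using medical grade double sided tape and a latex medical wrap". No alternative wrap is offered. Section 6.7a adds, for PD patients only, an external accelerometer adhered to the back of the hand.

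Section 6.4b has four exclusions:

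- The first concerns other neurologic disease, or PD together with ET.
- The second is about sensation at one device site: "Symptoms of peripheral neuropathy at the wrist (reduced vibratory, pinprick, or temperature sensation".
- The third sets a cognitive threshold on the MoCA, or a prior dementia diagnosis.
- The fourth is about mobility: "Unable to walk without a walking aid (e.g. cane, stick, walker".

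The one inclusion criterion specific to dystonia, in 6.4a, concerns posture: "For patients with dystonia, they will have abnormal dystonic postures of the head and not isolated head tremor".

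On skin effects, section 10 says that "there is the possibility of minor skin irritation at the site where the wearable devices are placed". It adds that irritation might outlast the test session, in which case the patient is told to seek routine care, and that unknown risks are possible. Section 8 mentions skin irritation as a reason for stopping early and attributes it to vibration.

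**The concern.** The protocol names a specific material, latex, and a specific site, the neck, and also uses adhesive tape there. Allergy to either material can be known in advance and asked about in one question. The eligibility criteria do not ask, and the risk section does not mention the fixing material.

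The exposure comes from how the device is held in place. It adds nothing to the scientific question, and another material could hold the device. The reassurance in section 10 does not reach this exposure. It rests on vibration weaker than that of commercial massagers and on an absence of adverse events in earlier device testing. The first argument is about vibration, not about tape or wrap. The earlier testing described in 6.5 was in patients with PD and resting tremor, plus a small number of patients at the site; the text does not say whether any of them wore the device on the neck or under latex.

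At stake is the safety of a few volunteers, and the completeness of the risk description.

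**Working it through.** The plan gives no figure on this point, so the check is a comparison of sections.

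**Step 1: who is exposed to what.** Group sizes are from 6.2, attachment from 6.5, 6.7 and 6.7a.

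- PD, 30 patients: stimulators on bands at wrist and/or ankle; accelerometer adhered to the hand. Adhesive yes; latex not stated.
- ET, at most 5: stimulators at wrist and/or ankle; section 6.7b lists only rating scales. Neither adhesive nor latex stated.
- Dystonia, at most 5: stimulators taped and wrapped on the neck. Adhesive yes; latex yes.

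Planned maximum: 30 + 5 + 5 = 40. Stated latex contact: at most 5 of 40, or 12.5%. Stated adhesive contact: at most 30 + 5 = 35 of 40.

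**Step 2: do the criteria screen for it?** The four exclusions in 6.4b cover other neurologic disease or coexisting PD and ET, sensory symptoms at the wrist, cognition, and walking aids. The inclusion criteria in 6.4a cover age and consent, diagnosis, stable medication, ET tremor score and dystonic posture. None refers to latex, adhesive, allergy or skin. The only criterion tied to a device site is the wrist one, and its subject is sensation.

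**Step 3: does the screening procedure add it?** Section 6.6 has personnel read a telephone script giving study details and the inclusion and exclusion criteria. No allergy question is described.

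**Step 4: does the risk text cover it?** Section 10 foresees unpleasant stimulation and minor skin irritation at the device site. Section 8 links irritation to vibration. Neither mentions allergy or the fixing material. Latex occurs in the supplied text only in the 6.7 sentence quoted above.

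**Result.** A dystonia patient with a known latex or adhesive allergy who meets the other criteria passes 6.4 as written, and 6.7 as written then applies tape and latex. The same holds for a PD patient with a known adhesive allergy and the hand accelerometer.

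The chance that such a patient enrols cannot be derived: the documents give no prevalence, and the gap in the criteria does not depend on one.

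**The case against.** The strongest reply is that eligibility on paper is not the same as exposure in practice. Neither the telephone script nor the consent form is among the documents reviewed, so either may ask about allergy. Candidates come through clinic providers who raise the study only where appropriate, coordinators have access to medical records, and patients who know of an allergy may say so. This stands as a limit: a reader might infer that the site would accept and wrap an allergic patient, and the documents do not support that. It does not close the gap, because the only described content of the script is study details and the criteria themselves.

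Other stronger readings also fail:

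- **Hours of latex contact.** The 4 hours in 6.7 is the maximum visit length for the study. The same section gives dystonia patients a shorter, narrower assessment, and 6.7c lists only five TWSTRS items and the CGI-I. No wrap time is stated.
- **A reaction counted against vibration.** The supplied text has no rule for attributing adverse events, and section 7 plans no adverse-event analysis.
- **Loss of one fifth of the dystonia group.** Section 10 gives patients the option to stop, and sections 8 and 10 treat partial data as useful. Section 7 limits this group to measures of central tendency, with no efficacy test, so no powered result is at risk.
- **A latex exclusion for every group.** Latex is stated only for dystonia, so this would exclude people for no shown reason. Nothing in the documents calls for a broken-skin exclusion either.

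It is also fair to say that section 10 does foresee skin reactions at the device site. It is incomplete because it leaves out allergy to the fixing material.

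**Conclusion.** The point holds as a minor safety improvement. The attachment method in 6.7, the criteria in 6.4 and the risk text in section 10 do not fit together: a named material is used on the neck, yet known allergy to it neither excludes a patient nor appears as a risk. A patient with such an allergy is eligible on the listed criteria and could be exposed.

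Its size is at most 5 participants for latex and at most 35 for adhesive. The sample size, the PD analysis and the descriptive aims for ET and dystonia are untouched. The conclusion assumes that the criteria in 6.4 are the complete list; if the script or the consent form already contains an allergy question, what remains is to bring the protocol into line with it.

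**What to change.** Three edits:

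1. **Section 6.7.** Specify a latex-free wrap for the dystonia group. If latex is kept, add known latex allergy to 6.4b as an exclusion for that group only; with a latex-free wrap that exclusion is unnecessary.
2. **Section 6.4b.** Exclude known allergy to medical adhesive where a device or sensor is adhered to skin: the neck in dystonia and the hand accelerometer in PD. Since the script conveys the criteria, the question then reaches telephone screening.
3. **Section 10.** Name reaction to the fixing material, tape or wrap, as a risk separate from any effect of vibration.

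The cost is a different consumable, a line or two of text and an occasional screening failure. Section 6.2 already plans to consent about 50 people for up to 40 places. The intervention, outcomes and analysis stay as they are.

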#### Baseline testing:

MDS-UPDRS: Select measures from the motor section of the Movement Disorders Society Unified Parkinson's Disease Rating Scale (MDS-UPDRs). The MDS-UPDRS is a revision of the Unified Parkinson's Disease Rating Scale (UPDRS) originally developed in the 1980s. The scale is used in the clinic as well as in research to measure PD symptom severity. Individual measures are rated as 0 (normal) to 4 (severe).

Montreal Cognitive Assessment (MoCA): The MoCA is a cognitive screening test designed to assist Health Professionals in the detection of mild cognitive impairment and dementia. It will be used to exclude patients with cognitive impairment significant enough to confound the research variables of interest.

6.7a: Outcomes to be measured in subjects with PD:

Quantitative Tremor Assessment: An external accelerometer (Delsys Trigno; <https://delsys.com/trigno/>) will be adhered to the skin of the dorsum of the hand and will be used to quantify displacement of the hand due to tremor in the settings listed below. Delsys Trigno sensors have been used in multiple prior UF IRB approved studies and is FDA and CE registered with FCC ID, and is certified IEC601-1 (General Requirements for Medical Devices) and IEC601-1-2 (electromagnetic compatibility requirements for Medical Devices) with a UL recognized Internal Battery.

- 1. Sitting at rest
- 2. Sitting with both arms outstretched
- 3. Sitting at rest while performing a distracting cognitive task (reciting the months of the year backwards)
- 4. Transition from rest to posture (arms held directly in front of patient) for 10 seconds

Kinesia One accelerometer: The following select measures of MDS-UPDRS Part III: Motor Examination will be repeated before and during VTS:

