## **5. Specific Aims:**

**Specific Aim. Evaluate the feasibility, reliability, and clinical effects of VTS on basic tasks of motor control and on the motor symptoms of patients with movement disorders.**

Hypothesis: VTS will produce beneficial effects on basic tasks of motor control and abnormal motor symptoms in patients with movement disorders. VTS Settings will include continuous stimulation between 60-120 Hz, intermittent stimulation at  $\frac{1}{2}$  baseline step frequency during walking, and sham stimulation (2 seconds of 30 Hz stimulation only at stimulation onset).

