## **7. Outcome and Statistical Approaches:**

For essential tremor and dystonia, the aims of this unblinded pilot study are to identify the optimal settings of VTS that are most promising to be tested in future clinical trials, statistical analysis will be limited to basic measures of central tendency. We will compare scores and values on the individual outcome measures listed above both on and off VTS, and within disease group means for each measure will be used to help guide the choice of settings to be tested in future studies. This pilot study will not be powered for between disease groups analysis or to test the efficacy of VTS for ET, or dystonia.

For Parkinson's disease, we expect to have data sufficient to justify exploratory statistical analysis. We have estimated that the number of patients included will allow for statistical analysis of patient's task performance before and during VTS. This was based on a medium effect size (Cohen's  $d = 0.50$ ) for the comparison of tremor power during VTS versus baseline. With an alpha of 0.05 and power of 0.80, the required sample size is 27 (based on a one-sided paired sample t-test). Thus, by recruiting 30 participants with PD, our sample size will give us sufficient statistical power to detect an effect with medium effect size. Statistical analysis will consist of a repeated measures ANOVA on the change in tasks performance scores relative to baseline. All post-hoc analyses will be corrected for multiple comparisons using Bonferroni correction.

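### The distraction tremor recording repeats one fixed, unscored recitation after a baseline that comes first, so a practice effect could be read as a VTS effect in the before/during comparison

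*Combined protocol and SAP*

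**What the plan says.** Section 6.7a lists four accelerometer recordings of hand tremor in PD. The third is "Sitting at rest while performing a distracting cognitive task (reciting the months of the year backwards". No other distractor is named. The section mentions no alternate form, no rehearsal before the first recording, and no scoring of the recitation.

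Section 6.7 says that the visit includes "motor tasks and clinical tests (described in detail below) both on and off VTS", and that "Testing will occur over the course of a single day at the Fixel Institute for Neurological Diseases". It fixes the order of the tasks ("Outcomes to be measured are described below in the order that they will be tested") but says nothing about the order of the VTS settings. Section 5 includes among those settings "sham stimulation (2 seconds of 30 Hz stimulation only at stimulation onset".

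Section 7 describes the PD analysis as "statistical analysis of patient's task performance before and during VTS", which puts the baseline recording first. It then states: "Statistical analysis will consist of a repeated measures ANOVA on the change in tasks performance scores relative to baseline". The sample size rests on tremor power, VTS against baseline, with a one-sided paired t-test. Section 7 does not say which of the four recordings supplies tremor power, and it names no active-versus-sham contrast.

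**The concern.** A distractor is useful in a tremor recording only if it imposes a comparable load each time. Here the load is one short, fixed sequence, met first at baseline and again during VTS within hours. If patients find it easier the second or third time, the baseline carries the heaviest load and the VTS recordings a lighter one. If tremor also rises with load, it would then fall from baseline without any effect of the device.

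Because the recitation is not scored, nobody could tell afterwards whether the load had stayed equal. Elsewhere the plan does guard against predictability: in the reaction time task of Section 6.7a, the delay before the signal is varied.

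At stake is how this one recording is read when settings are chosen for later trials. Section 6.5 reports that a setting intended as sham in the previous study appeared to reduce resting tremor in about 60% of patients. The protocol attributes this to inadequately investigated settings, not to practice. It still shows that a fall under a control setting is a practical problem of interpretation here.

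**Working it through.** **1. The plan's own figure.** Inputs from Section 7: standardised effect d = 0.50, one-sided alpha 0.05, power 0.80, paired t-test. Power is P(T > t(0.95, n − 1)), where T is noncentral t with n − 1 degrees of freedom and noncentrality d√n.

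- n = 27: noncentrality 0.50 × √27 = 2.60; power 0.812. This is the smallest n with power of at least 0.80, so the stated 27 reproduces.
- n = 30 (Section 6.2): noncentrality 0.50 × √30 = 2.74; power 0.848.

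The present point leaves the sample size unaffected.

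**2. Where a practice effect enters.** For the distraction recording, write the expected tremor at baseline as μ. Under setting s write it as μ + τ_s + p_s, where τ_s is the VTS effect and p_s is any shift due to repetition or time since baseline.

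- Change from baseline: (μ + τ_s + p_s) − μ = τ_s + p_s. The two parts cannot be separated.
- Active change minus sham change: (τ_A + p_A) − (τ_S + p_S) = (τ_A − τ_S) + (p_A − p_S). The baseline cancels, and so does any shift common to all later recordings.
- What remains, p_A − p_S, depends on the order of settings. With balanced order it averages to about zero, provided that position effects add to setting effects and nothing carries over from one setting to the next.

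The exposure therefore lies in the before/during comparison. The active-versus-sham comparison largely escapes it, but Section 7 does not specify that comparison and no section states the order.

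**3. Illustration of size.** The documents give no practice effect, so the drift δ, in SDs of the within-patient change, is an assumption. Take no VTS effect, n = 30 and a single one-sided test at 0.05. The rejection rate is the noncentral-t tail with 29 degrees of freedom and noncentrality δ√30.

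| Assumed drift δ | Noncentrality | Rejection rate, n = 30 | Rejection rate, n = 27 |
|---|---|---|---|
| 0 | 0 | 0.05 | 0.05 |
| 0.1 | 0.55 | 0.134 | 0.127 |
| 0.2 | 1.10 | 0.283 | 0.263 |
| 0.3 | 1.64 | 0.484 | 0.450 |

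The noncentralities are for n = 30. The rates assume that the drift favours VTS. They apply to the test used for sizing, run once on this recording without correction. They do not apply to the planned repeated measures ANOVA with Bonferroni-corrected post-hoc tests.

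**The case against.** The strongest reply is that the mechanism is not documented. A reader might infer that the recitation does become easier and that the bias therefore runs towards benefit. No section reports a practice effect for this task, or lower tremor when it is easier. Other influences could act in the opposite direction: Section 10 anticipates fatigue, and Section 6.7 describes a visit of up to 4 hours off medication. This stands. The net drift could have either sign.

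Second, a reader might infer that balancing the settings would not help because the baseline always comes first. That is true of change from baseline taken alone. It is not true of a comparison between settings. If setting is the within-patient factor in the ANOVA, which is a natural reading, the shared baseline cancels as shown in the working. This stands too, but Section 7 names neither the factor nor the contrast, so the protection is available and not secured.

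Third, the finger tapping, reaction time, pegboard and walking tasks are also repeated on and off VTS, so practice is a general feature of a baseline-first design. That is fair. The distraction recording differs in that the recitation is there only to impose load, and its performance is not recorded.

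Fourth, a constant distractor is a legitimate way to standardise load, and serial subtraction from new starting numbers might become easier with practice as well. This also stands, and it is why alternate versions are only optional in the fix.

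**Conclusion.** The point holds in a limited form. For the distraction recording, one of four tremor recordings in PD, the plan cannot separate practice or time from VTS in the before/during comparison, and it collects nothing that would show whether load stayed equal.

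For this to produce a false benefit, two assumptions must both be true: that the recitation becomes easier with repetition, and that tremor rises with cognitive load. The documents support neither with a figure. It is also an inference, though a fair one, that the recitation is repeated under every setting, because no schedule by setting is given.

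The rates of 13%, 28% and 48% show only what an assumed drift of 0.1 to 0.3 SD would do to a single one-sided paired t-test at n = 30. A reader might take them as the trial's false-positive rate. The documents do not support that: the planned analysis is the ANOVA, the drift is assumed, and Section 7 does not say that tremor power comes from this recording. The PD analysis is exploratory and the sample size is unaffected. This is a worthwhile low-cost improvement, not a serious flaw.

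**What to change.** In Section 6.7a, item 3, add one practice run of the recitation before the baseline recording, and log items completed and errors in each condition. The practice run reduces any early gain, and the log lets equal load be checked.

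In Section 7, state that this recording will be interpreted by active versus sham change and not by change from baseline alone. State also how the order of the settings is balanced, since the comparison relies on it.

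Equivalent alternate versions of the distractor, rotated across conditions, are optional. They would not by themselves remove general practice, and the versions may differ slightly in difficulty.

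Cost: a few lines of text, a short entry on the recording form and about one extra minute per PD patient, with no extra staff.
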